17.1.2. MISSING DATA METHODS FOR PRIMARY EFFICACY VARIABLE

Subjects who 1) discontinue the study for worsening of disease, lack of efficacy, or adverse event related to EoE, 2) use a rescue medication for EoE, or 3) have rescue medical procedure during the study as confirmed after blinded review by clinical and medical team members before study unblinding will be considered to have a missing outcome in the analysis of all efficacy endpoints at any subsequent timepoints, including the primary endpoint. The rescue medications/rescue medical procedure will be identified by the Pfizer clinical team during blinded data review. The detailed information regarding the identification of rescue therapy is provided in Appendix 4. In scenarios 2 and 3 above, if a subject has an efficacy measurement collected after the initiation of rescue medication/rescue medical procedure, the observed data will be censored at the time of initiation and they will be considered as having a missing outcome. Subjects in all 3 scenarios above may still be included in the respective Per Protocol Set, provided they do not violate other criteria for Per Protocol Set. For example, they will be excluded from the respective Per Protocol Set if they initiate a prohibited medication before the Week 16 efficacy assessment that can affect efficacy of the study treatment and the indication is unrelated to EoE.

Analysis visits will be mapped as per Section 6.4 before any missing data imputation method is applied.

Subjects who initiate rescue medication will have PEC results after the start of rescue medication/rescue medical procedure set to missing. All missing PEC at Week 16 and Week 24 will then be imputed using multiple imputation under missing at random (MAR) procedure with a fully conditional specification (FCS) and predictive mean

matching for PEC as the primary missing data method. There are two different types of missing data patterns: non-monotone and monotone. A subject with missing data at any post-Baseline visit, and a non-missing data point after that visit is said to have intermittent missing data (non-monotone). A subject with missing data at any post-Baseline visit and at all subsequent visits is said to have monotone missing data.

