^b No missing data methods will be implemented since missing data will be handled in the linear mixed effect model.

^c Subjects who initiate rescue medication/rescue procedure will have assessments collected after the rescue medication/rescue procedure is initiated set to missing.

^d Subjects who initiate rescue medication/rescue procedure will have assessments collected after the rescue medication/rescue procedure is initiated set to missing. Missing data for any reason will be considered as nonresponder. Adjusted difference and p-values are based on the estimated common risk difference using the MH weights

^e Subjects who initiate rescue medication/rescue procedure will have assessments collected after the rescue medication is initiated set to missing. Missing data will be imputed using multiple imputation.

^f primary approach (14-day period approach) will be used to calculate DSQ total score

^g sensitivity approaches (14-day period: worst case scenario approach and 7-day period approach) will be used to calculate DSQ total score.

In addition, some of the additional analyses above will be conducted as follows:

Percent change from baseline in esophageal PEC at Week 16 above will be repeated at week 24 using the same ANCOVA model.

Change from baseline in DSQ total score at Week 16 above will be repeated for week 2, 4, 6, 8, 10, 12, 14, 20 and 24 in Double-Blind Treatment Period, using the same linear mixed effects model for change from baseline in DSQ total score at Week 16.

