APPENDIX 4. IDENTIFICATION OF RESCUE THERAPY

This appendix outlines the process the Pfizer clinical team/medical reviewers will use to determine rescue therapy for EoE in the APD334-206 study.

The objective of rescue therapy identification is to establish 1) intercurrent events for the efficacy estimands, and 2) exclusion of subjects from the Per Protocol Set(s).

Per protocol, rescue therapy is defined as any new therapy (ie, medication or procedure) or change in existing EoE therapy used to treat new or worsened EoE symptoms. In addition, use of certain medications/procedures that do not meet the definition of rescue therapy but are deemed to have significant impact on the efficacy assessment will be reviewed and may be considered as rescue therapy.

Only therapies reported on the electronic case report forms (eCRFs) will be assessed for rescue therapy determination. Use of rescue therapy during the follow-up period (beginning on or after the date of last study treatment administration) will not be considered as a rescue therapy.

The list of all rescue therapy uses in the study will be identified and finalized prior to study unblinding.

Medical procedure

- Esophagogastroduodenoscopy (EGD)
 - o Rule:
 - When dilation was done during EGD, any after first dose
 - When dilation was not done during EGD, any EGD with food bolus removal after first dose

Medications

- Proton Pump Inhibitors
 - o Examples of Medications
 - Omeprazole (Prilosec)
 - Lansoprazole (Prevacid)
 - Dexlansoprazole (Dexilant)
 - Esomeprazole (Nexium)
 - Pantoprazole (Protonix)
 - Rabeprazole (Aciphex)
 - o Rules
 - When used for EoE: any new initiation or change in dose after Day 1
 - When used for other disease (eg, GERD): New initiation or change in dose after Day 1 AND
 - Use > 4 weeks at the time of EGD OR
 - Use > 8 weeks with the end of treatment date falling within 4 weeks of EGD
- Corticosteroids
 - o Applicable route of administration: swallowed, oral, IM, SC, IV
 - o Examples of Medications
 - Fluticasone (Flovent)
 - Budesonide (Pulmicort, Flexhaler)
 - Betamethasone
 - Cortisone
 - Deflazacort
 - Dexamethasone
 - Fludrocortisone
 - Hydrocortisone
 - Methylprednisolone
 - Prednisone
 - Prednisolone

- Triamcinolone
- Rules
 - When used for EoE: any new initiation after Day 1
 - When used for other diseases: any new initiation after Day 1 AND
 - Use > 7 days at the time of EGD OR
 - Use > 14 days with the end of treatment date falling within 8 weeks of EGD

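### SAP Appendix 4 judges non-EoE PPI and steroid courses at an unnamed EGD while SAP 17.1.2 censors from the start date, so drug use after Week 16 can remove an observed Week 16 PEC

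*SAP*

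**What the plan says.** SAP Appendix 4 brings some courses of drugs taken for other diseases into rescue therapy. A PPI newly started, or changed in dose, after Day 1 counts if it meets either of two conditions. The first concerns a course still running: "Use > 4 weeks at the time of EGD OR". The second concerns one that has already finished: "Use > 8 weeks with the end of treatment date falling within 4 weeks of EGD". A newly started corticosteroid has the same pair with other limits. For current use the wording is "Use > 7 days at the time of EGD OR", and a finished course falls under "Use > 14 days with the end of treatment date falling within 8 weeks of EGD". None of the four conditions names the EGD. Protocol Appendix 1 schedules post-baseline EGDs at Weeks 16 and 24 (or early termination) in the double-blind period and at Weeks 32 and 52 in the extension.

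The appendix produces one study-wide list, not a flag per visit: "The list of all rescue therapy uses in the study will be identified and finalized prior to study unblinding".

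Censoring runs from the start of the drug. SAP 17.1.2 says "the observed data will be censored at the time of initiation and they will be considered as having a missing outcome" and, for PEC, "Subjects who initiate rescue medication will have PEC results after the start of rescue medication/rescue medical procedure set to missing". The footnotes to the table of planned analyses in SAP 17.2.1 say that such subjects "will have assessments collected after the rescue medication/rescue procedure is initiated set to missing". The estimand table in SAP 2.4 treats rescue before Week 16 as nonresponse for both histologic responder endpoints.

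**The concern.** The classification looks at an EGD, but the censoring looks at a start date. With two post-baseline EGDs in the double-blind period, one course can fail the condition at Week 16 and meet it at Week 24. Once listed as rescue, it is censored from initiation, which may precede the Week 16 biopsy. What the subject did after the primary endpoint was measured would then decide whether that measurement enters the analysis.

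The Week 16 PEC is the primary endpoint. A value lost this way is replaced by multiple imputation under missing at random, fitted separately by arm (SAP 17.1.3). The Week 24 PEC is censored too, so no post-baseline count of the subject's own informs the imputation. The Week 16 DSQ score is also lost, because SAP 17.1.2 covers all efficacy endpoints. A subject who met PEC < 15 or ≤ 6 at Week 16 is scored as a failure.

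**Working it through.** There is no plan figure to reproduce; the check is date arithmetic on the rules.

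**Inputs.** Week 16 EGD on Day 113 and Week 24 EGD on Day 169, each ± 5 days (SAP 6.4). PPI conditions: more than 28 days at EGD, or more than 56 days and ended within 28 days of EGD. Steroid conditions: more than 7 days at EGD, or more than 14 days and ended within 56 days of EGD (Appendix 4). Planned N of 96, randomized 3:3:2 (SAP 3.1). Use at EGD is taken as EGD day minus start day.

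**Two subjects, same PPI for reflux started on Day 95.**

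| | Continues past Week 24 | Stops on Day 120 |
|---|---|---|
| Use at Week 16 EGD | 113 − 95 = 18 days | 113 − 95 = 18 days |
| Qualifies at Week 16? | No (18 ≤ 28) | No (18 ≤ 28) |
| Use at Week 24 EGD | 169 − 95 = 74 days | 120 − 95 = 25 days in total, already stopped |
| Qualifies at Week 24? | Yes (74 > 28) | No (neither > 28 nor > 56 days) |
| Week 16 PEC (Day 113) | After Day 95, so set to missing | Kept |

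Exposure at the Week 16 biopsy is the same in both.

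**PPI start days exposed.** Not qualifying at Week 16 needs 113 − start ≤ 28, so Days 85 to 112: 28 start days.
- Still in use at Week 24: 169 − 112 = 57 to 169 − 85 = 84 days, all above 28, so every such course qualifies.
- Stopped before Week 24: qualifies if used for more than 56 days and stopped on Day 169 − 28 = 141 or later, that is Days 141 to 168.
- Visit windows: a Week 16 EGD on Day 108 or 118 moves the range to Days 80 to 107 or 90 to 117, still 28 days. The shortest gap between the two EGDs is 164 − 118 = 46 days, above 28, so the Week 24 result holds.
- Counting both end days, as SAP 15.1 does for exposure, makes a Day 85 start 29 days at Day 113. The range becomes Days 86 to 112, 27 days.

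**Steroid start days exposed.** 113 − start ≤ 7 gives Days 106 to 112 (Days 107 to 112 if counted inclusively). A course of more than 14 days from there ends on Day 120 or later.
- If the 8-week window means before the EGD, the Week 24 window opens on Day 169 − 56 = 113. Every such course qualifies at Week 24 and not at Week 16.
- If an end date after the EGD also counts, the Week 16 window reaches Day 113 + 56 = 169. A course ending by then already qualifies at Week 16, and the mismatch disappears for it. Only a course running past Day 169 would be left, and the point does not rest on that.

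**Size per subject.** Arms of 96 × 3/8 = 36, 36 and 96 × 2/8 = 24. One responder turned nonresponder moves the rate by 1/36 = 2.8 points on an etrasimod arm or 1/24 = 4.2 points on placebo.

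**The case against.** The strongest reply is that nothing is deleted automatically. Appendix 4 says that uses outside the strict rescue definition are reviewed and may be counted, and SAP 17.1.2 requires blinded confirmation. A team could read the EGD as the one being assessed. The Per Protocol Set rule (SAP 5.5) already ties rescue to an effect on the Week 16 endpoint. This stands as far as it goes: the loss is the literal result of two rules, not a stated intention. But no text tells the reviewers to work EGD by EGD, and the FAS censoring rule has no Week 16 qualifier.

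The numbers are also likely to be small. Existing PPI therapy is to stay stable (Protocol 6.7.2), and systemic steroids other than short or pulse courses are prohibited on treatment (Protocol 6.7.3). Protocol 11.4.2 plans an observed-data analysis regardless of rescue, which would show any influence without repairing the primary analysis.

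A reader might infer more than the documents support:
- That the appendix declares short use harmless to the biopsy. It sets classification thresholds and says nothing about absence of effect.
- That a quarter of subjects are exposed, because 28 of the 111 possible start days from Day 2 to Day 112 is 25% (7 of 111, 6%, for steroids). These are shares of calendar days, not of subjects or courses.
- That the Week 32 EGD can do the same. A PPI course in the exposed range that does not qualify at Week 24 has stopped after 56 days or fewer and never qualifies, so Week 32 adds nothing unless the Week 24 EGD is missing.
- That the loss favours one arm. The documents give no information on this.

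**Conclusion.** The mismatch is real on the text and reaches the primary endpoint and both histologic responder endpoints. It is firm for PPIs started on about Days 85 to 112 (one day fewer with inclusive counting) that are still in use at Week 24, or were used for more than 8 weeks and stopped within the 4 weeks before it. For steroids started on about Days 106 to 112 it depends on the 8-week window meaning before the EGD, which the SAP does not say.

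This rests on nominal visit days, on the literal combination of Appendix 4 and SAP 17.1.2, and on the blinded review applying it that way. The number of subjects cannot be derived from the documents; 0 to 3 of 96 is an assumption, and its lower end is no effect. The per-subject shift of up to 2.8 or 4.2 points applies only to a subject who was a responder at Week 16. The point is worth correcting because a prespecified rule should not let post-endpoint behaviour decide whether a primary-endpoint value is used.

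**What to change.** In SAP Appendix 4, with a cross-reference in SAP 17.1.2 and 2.4:
- State that, for drugs used for other diseases, rescue status is decided separately at each scheduled EGD. A course that first qualifies at a later EGD makes PEC missing and histologic response a nonresponse from that EGD onward; earlier EGDs stay as observed. In the Day 95 example the continuing subject keeps the Week 16 PEC and loses only Week 24.
- State whether the 4-week and 8-week windows mean before the EGD, and whether days are counted inclusively.
- State the matching DSQ rule, since DSQ is scored every two weeks and not at EGDs: the Week 16 score is kept when the course does not qualify at Week 16, and a date is named from which later scores are censored.
- Keep censoring from initiation for EoE rescue and for procedures, and leave the clinical thresholds as they are.

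The cost is a few sentences and a by-visit flag in the blinded review. No new data are needed, but it must be settled before the rescue list is finalized.
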